volume multiplied by ventilatory frequency) and expiratory tidal volume. In both groups of patients Com_{dyn} will be measured after delivery, but before RM (baseline measurement), and then 3, 10 and 20 minutes after the RM. At the same time points arterial blood pressure (systolic, diastolic and mean), heart rate, SpO₂, blood gas, ETCO₂, P_{peak}, expiratory tidal volume and minute volume will be measured too. SpO₂ and blood gas will be also measured postoperatively (10 minutes after extubation). Tables 2 and 3 present the basic patient's measurements. Data analysis example comes from preliminary data analysis before the beginning of the study.

Follow up measurements

Patients will be followed up for postoperative respiratory failure, which is defined as the need for non-invasive ventilation and/or mechanical ventilation after extubation. In cases of respiratory failure, the possible pulmonary complications are also being defined: pneumonia, atelectasis, pulmonary embolism, pneumothorax, acute lung injury (ALI), asthma, non-cardiogenic pulmonary oedema and severe hypercapnia. The routine postoperative oxygen use will also be noted and will be applied for half an hour postoperatively.

Statistical analysis

Before the beginning of the study, and for **determination of sample size**, we will conduct **power analysis**, in an attempt to estimate the sample size required so that the study would have adequate power to detect clinically meaningful differences between the two study groups with regards to lung compliance (dv/dp), which is the primary outcome of the study. For this analysis, we used the G*Power Software that is freely available online at <http://www.gpower.hhu.de/en.html> from the Psychology Department of the University of Dusseldorf, in Germany.

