Our power analysis is based on previous studies but is even more generous^{17,22}. The required sample size calculation was based on the following assumptions: Clinically meaningful difference between the two groups is 20% of the mean value, and SD of the observed lung compliance is 25% of the mean value (rather generous), therefore size effect $d = 20\% / 25\% = 0.8$, with two-sided testing, with $\alpha = 0.05$ and $b = 0.1$ (therefore, power = $1 - b = 0.9$). Under these assumptions, G*Power indicated that we will need minimum 34 patients per group for this study to have adequate power. To confirm accuracy of this calculation, we will also conduct sample size estimation using the Statistica v 7.0 Statistical Software package (StatSoft Inc, Tulsa, Oklahome, USA), in order to find out if this confirmatory analysis will produce identical results. Finally we will confirm our results using the suitable mathematic formula (see [appendix 2](#)).

In order to allow for possible protocol violations, errors, patient attrition or other study shortcomings, we will enroll 45 patients in each arm of the study (about 10 women more in each group of patients). As pregnant women are a very “sensitive” population and we are afraid of much protocol violation (removal women from protocol mainly due to hemodynamic instability) we will chose to randomize 45 women per group, which is a generous number.

We will check if data are normally distributed (Kolmogorov Smirnov and Shapiro Wilks test). Ventilatory and haemodynamic data and intraoperative and postoperative variables (all continuous variables) will be presented as mean values (+/- SD). Data will be compared between and within groups using Mixed Analysis of Variance (Mixed Anova-General Linear Model) if are normally distributed or with Kruskal Wallis test in case that we do not have normally distributed data.

Bonferoni correction will be used for multiple comparisons correction. In order to check and supplement our Mixed Analysis of Variance we will also use two-sample t-test to compare the two groups at each time point (for ventilatory and haemodynamic variables). Patient and procedural characteristics will be compared between groups using chi-square test for categorical variables and independent-sample t-test for continuous variables. Two tailed P-values <0.05 will be considered statistically significant. For data analysis SPSS statistical software version 22 will be used.

Patients Records

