Table 1: Patient characteristics presented as mean (SD) or n=number of patients. Intra- and post-operative characteristics presented as mean (SD).

Patient Characteristics	RM Group n=45	Control Group n=45
Age (yrs.) [mean (SD)]	A1	B1
BMI (kg/m ²) [mean (SD)]	A2	B2
Smoking status (n)	A3	B3
Intraoperative Characteristics		
Duration of anesthesia (min)	A4	B4
Time to delivery (min)	A5	B5
Crystalloids (ml)	A6	B6
Colloids (ml)	A7	B7
Blood (units)*	A8	B8
Ephedrine dose (mg) ⁺	A9	B9
Postoperative Characteristics		
Length of hospital stay (days)	A10	B10
Pulmonary complications (n)	A11	B11
Pneumothorax (n)	A12	B12
Pneumonia (n)	A13	B13
Other (n)	A14	B14

Efficacy and Safety issues:

The efficacy of the RM to improve lung compliance and gas exchange will be the main efficacy issues of the study. The investigators believe that the Com_{dyn} (dv/dp) will be statistical significantly improved in the RM group compared to the control group (statistical significant difference between groups). A 20% increase in mean Com_{dyn} in the RM group compared to the control group would be clinically significant. This change in lung compliance perhaps would not have any significant impact for the majority of the patients of our study (young and healthy patients). However, underlying comorbidities may amplify changes in lung and cardiovascular physiology and anaesthesia may serve as a 'second-hit' that worsens patient outcome. For this reason a RM and the application of protective lung ventilation (low tidal volumes and PEEP) perhaps should be the suitable anesthetic practice for all the patients.

The investigators also believe that there would be statistical significant difference within groups too. In the RM group possibly there would be a difference in lung compliance (increase) between baseline and all the other time points (3, 10 and 20 minutes after the RM). Again a 20% increase in Com_{dyn} would be clinically significant, at least for some patients.

The investigators believe that the recruitment manoeuvre will improve the intraoperative and/or postoperative PO_2 , the PO_2/FiO_2 and the SpO_2 . Again for the population of our study (all women have a baseline $PO_2/FiO_2 > 400$) this improvement will not have a significant impact. All the data will be presented in tables 2 and 3 (**see next example with preliminary data analysis**).

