For safety issues we decided to perform a preliminary data analysis before the beginning of the study. We used 7 patients in each group, and we will use these data analysis as an example of our data presentation plan and to show the most important measurements of our study. At all time points (3, 10 and 20 minutes) after intervention there is a significant difference in Com_{dyn} between the two groups ($p < 0.001$). The Com_{dyn} is much higher in the RM group vs control group (table 2). The significant difference in lung Com_{dyn} depicts in figure 1a too.

Post intervention the peak inspiratory pressure at all time points (3, 10 and 20 minutes) is significantly lower in the RM group compared to control group ($p = 0.021$, table 2, figure 1b).

PO_2/F_iO_2 and PO_2 are also significantly higher in the RM group vs the control group ($p < 0.001$) at all time points post intervention (3, 10 and 20 minutes) while PO_2 is also significantly higher in the RM vs control group postoperatively ($p < 0.001$). SpO_2 is significantly difference between the two groups at 10 and 20 minutes post intervention and postoperatively ($p = 0.04$) – table 2

There are no significant differences in expiratory tidal volume, minute volume, end tidal CO_2 , PCO_2 and in hemodynamic data between the two groups (tables 2, 3).

[figure not shown]
Table 2. Respiratory Mechanics and Gas Exchange in the two groups of pregnant women (recruitment vs control, respectively-**Example**). Data are presented as mean \pm SD. The P-value corresponds to the tests of between subject main effects using the mixed Anova test (recruitment vs control group). The two groups were also compared separately at each time point using the independent two-sample t-test (*) and (**). (*) denotes significant differences from the control when $P < 0.01$ while (**) is used whenever $P < 0.05$. PaO₂, arterial blood oxygen; PaCO₂, arterial blood CO₂; SpO₂, arterial blood oxygen saturation; FiO₂, oxygen concentration.

	Baseline	After intervention (minutes)			Postoperative	P-value
		3 min	10 min	20 min		
Peak Inspiratory Pressure (cmH₂O)					-	0.021
Recruitment	23.9 (2.9)	19.9 (2.5)*	20.2 (2.9)*	20.3 (3.0)*		
Control	23.0 (2.8)	22.1 (2.8)	22.5 (2.7)	22.2 (2.7)		
Com_{dyn} (ml/cmH₂O)					-	<0.001
Recruitment	33.6 (6.8)	51.4 (12.8)*	49.9 (11.2)*	49.7 (10.9)*		
Control	31.1 (7.9)	29.6 (7.2)	30.6 (8.1)	30.9 (8.1)		
PaO₂ (mmHg)						<0.001
Recruitment	211.7 (10.6)	242.7 (26.9)*	242.1 (22.0)*	243.5 (27.6)*	108.4 (6.7)*	

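### If normality tests fail, the plan substitutes Kruskal-Wallis for the mixed ANOVA, but that test is not valid for comparing the same women across time

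*Protocol*

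**What the plan says.** Com_dyn "will be measured after delivery, but before RM (baseline measurement), and then 3, 10 and 20 minutes after the RM" (Secondary measurements), so each woman contributes four readings of the primary outcome.

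The Statistical analysis section first sets a check: "We will check if data are normally distributed (Kolmogorov Smirnov and Shapiro Wilks test"). It then states the analysis: "Data will be compared between and within groups using Mixed Analysis of Variance" if the data pass, "or with Kruskal Wallis test in case that we do not have normally distributed data". Kruskal-Wallis is the only substitute named, and the sentence applies it to both kinds of comparison.

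The within-group comparison is intended. Under Efficacy and Safety issues: "The investigators also believe that there would be statistical significant difference within groups too", with the RM arm expected to rise from baseline at 3, 10 and 20 minutes.

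The example Table 2 shows what the normal-data route reports: "The P-value corresponds to the tests of between subject main effects using the mixed Anova test". As a supplement, "we will also use two-sample t-test to compare the two groups at each time point". The threshold is "Two tailed P-values <0.05 will be considered statistically significant".

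**The concern.** Kruskal-Wallis compares independent samples. Readings from the same women at four times are not independent, so using the test across time discards the pairing. The stable differences between women then count as noise, and real changes within an arm become harder to see.

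Between arms the risk runs the other way. Table 2's P-value summarises all time points in one test of group. Kruskal-Wallis has no counterpart to that unless the readings are first reduced to one per woman, and the protocol does not ask for this. An analyst who fed it every reading would count each woman several times. Nor does the test give a group-by-time effect, which is the direct expression of an improvement that differs between arms.

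The choice between the two methods would be made from the trial data by a pre-test. The section does not say whether the check applies to raw values or residuals, to which arm-by-time cells, or what follows if the two normality tests disagree. A mixed ANOVA needs only roughly normal residuals, and with about 45 women per arm its comparison of means tolerates moderate departures.

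**Working it through.** **The plan's own figure.** The sample size reproduces. Appendix 2 gives n = 2 × (25/20)² × (1.96 + 1.28)² = 32.8, so 33. The noncentral t calculation for d = 0.8, two-sided 5%, power 90% gives 33.8, so 34, as stated. This point does not affect it. The protocol gives no figure for the fallback.

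**Inputs.**
- 45 women per arm and four readings each: protocol.
- Clinically relevant difference 20% of the mean and SD 25% of the mean: Statistical analysis. Efficacy and Safety issues applies the same 20% to the within-group rise. In SD units this is 20/25 = 0.8.
- Within-woman correlation rho: not given in the protocol. Assumed equal between all pairs of times, with results shown over a range.

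**1. Within one arm, four times, no true change.** If the pairing is ignored, the statistic behaves approximately as (1 − rho) times a chi-square on 3 degrees of freedom. The true error rate is then P(chi-square > 7.815/(1 − rho)).
- rho 0.3: cut-off 11.16, probability 1.1%
- rho 0.5: cut-off 15.63, probability 0.14%
- rho 0.8 and 0.9: cut-offs 39.1 and 78.2, probability effectively 0

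Simulation with normal data agrees: 1.3% at rho 0.3, 0.1% to 0.3% at rho 0.5 across repeated runs, and 0% at 0.8 to 0.9. Friedman's test, which respects the pairing, stays near 5%.

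**2. Power within one arm (simulated; all three post-intervention readings raised).**

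| Rise | Test | rho 0.5 | rho 0.8 | rho 0.9 |
|---|---|---|---|---|
| 0.3 SD (assumed) | Kruskal-Wallis | 13% | 3% | 1% |
| 0.3 SD (assumed) | Friedman | 43% | 81% | 99% |
| 0.8 SD (protocol's 20%) | Kruskal-Wallis | over 99% | 100% | 100% |
| 0.8 SD (protocol's 20%) | Friedman | 100% | 100% | 100% |

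Repeated runs moved these figures by no more than about three percentage points.

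**3. Between arms, one time point.** Simulated type I error is about 4% to 5.5%. With two groups the test is equivalent to the rank-sum test, so this use is valid.

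**4. Between arms, three post-intervention readings stacked as if independent.** The variance is understated by the factor 1 + 2 × rho, so the error rate is about 2 × [1 − Φ(1.96/√(1 + 2rho))].
- rho 0.5: 1.96/1.414 = 1.386, giving 16.6%
- rho 0.8: 1.96/1.612 = 1.216, giving 22.4%
- rho 0.9: 1.96/1.673 = 1.171, giving 24.1%

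Simulation gives about 17%, 23% and 24%.

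**5. Shape of the data.** SD/mean for Com_dyn in Table 2: RM arm 6.8/33.6 = 20.2%, 12.8/51.4 = 24.9%, 11.2/49.9 = 22.4%, 10.9/49.7 = 21.9%; control arm 7.9/31.1 = 25.4%, 7.2/29.6 = 24.3%, 8.1/30.6 = 26.5%, 8.1/30.9 = 26.2%. The SD grows roughly with the mean, so a log scale is a natural response to skewness.

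**The case against.** The strongest reply is that the trial is sized and argued as RM against control, and that Kruskal-Wallis between arms at one time point is sound. That stands. A reader might infer that every P-value from the fallback is wrong; step 3 shows otherwise. What remains is that the protocol neither confines the test to that use nor names anything else for the within-group comparison.

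Second, a reader might infer that the primary comparison carries a false-positive rate of 17% to 24%. The documents do not support this. Nowhere does the protocol say that readings will be stacked. Appendix 4 gives each time point its own column, and the supplementary t-tests are per time point. Stacking is not excluded either, so the figure shows what the open wording permits, not what is planned.

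Third, the low power figures belong to an assumed 0.3 SD rise. At the protocol's own 20% the loss disappears, and the preliminary rise in the RM arm, from 33.6 to 51.4, is larger still. The within-arm error is also conservative: it hides changes and does not invent them. All of this stands and limits the impact on Com_dyn. The same rule, however, covers the other ventilatory and haemodynamic variables, where changes may be small.

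Fourth, the problem needs the switch to occur. It is tempting to put a chance on that: eight arm-by-time cells each tested at 5% give 1 − 0.95⁸ = 34%. That rests on independent cells and on one failing cell being enough, and the protocol states neither, so the figure is not relied on here.

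**Conclusion.** The point holds in a limited form. As written, the fallback is not a valid replacement for the within-group comparison: for an assumed correlation of 0.5 to 0.9, a nominal 5% test has a true level of about 0.3% or less. The resulting loss of power is severe for small shifts and negligible at the 20% rise the protocol targets. Between arms the fallback is acceptable on one value per woman, but the wording leaves other uses open, and no use of it yields a group-by-time effect.

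These sizes rest on 45 women per arm, equal correlation between times and mostly normal simulated data. Skewed (lognormal) data at rho 0.7 gave the same pattern: 0% within an arm and 5% between arms at one time point. The defect has no effect unless the normality check triggers the switch. It does not show that the main RM-versus-control conclusion would be wrong. It is a stated rule that should be corrected before the data are analysed.

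**What to change.** In Statistical analysis:
- Delete the normality-test switch and the Kruskal-Wallis fallback. Keep the planned repeated-measures mixed ANOVA as the analysis in all cases.
- Judge residuals from the fitted model. If they are skewed, analyse log Com_dyn.
- As a rank-based sensitivity analysis between arms, apply the Wilcoxon rank-sum test to one value per woman: the mean of her post-intervention readings minus baseline.
- Within arms, use a paired rank test: Friedman, or signed-rank tests against baseline with the Bonferroni correction already planned.

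Adding baseline Com_dyn as a covariate would be a separate change, because the mixed ANOVA as described has none. The cost is protocol wording only: the sample size, measurements and data forms stay as they are.

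### The 34 per group is right for one unadjusted t-test, but the plan does not name that test as its primary analysis, so the stated 90% power cannot be matched to the planned analysis

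*Protocol*

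**What the plan says.** All references are to the Protocol.

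- **Sample size (Statistical analysis).** The effect is set as "Clinically meaningful difference between the two groups is 20% of the mean value" and the spread as "SD of the observed lung compliance is 25% of the mean value", so d = 0.8. With a two-sided 0.05 level and 90% power, "G*Power indicated that we will need minimum 34 patients per group for this study to have adequate power". Appendix 2 reaches 33 with the normal formula. Enrolment is 45 per arm, described as "about 10 women more in each group of patients", to allow for violations and attrition.
- **Endpoint (Primary end-point).** Improvement in Com_dyn, recorded at baseline and at 3, 10 and 20 minutes. No primary time or contrast is given.
- **Analysis (Statistical analysis).** A mixed ANOVA between and within groups, then "Bonferoni correction will be used for multiple comparisons correction", then two-sample t-tests at each time to check and supplement the ANOVA. The Abstract also calls these t-tests supplementary.
- **Reported test (Table 2 legend).** One between-subject main-effect P-value per variable. The table's time columns include baseline.
- **Reference for the 20% (Efficacy and Safety issues).** "A 20% increase in mean Com_{dyn} in the RM group compared to the control group would be clinically significant".

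**The concern.** A sample size statement carries meaning only for the test it was computed for. Here it was computed for one t-test at an unadjusted 0.05, and the analysis text names no such test as primary. Two features of that text can lower power below the stated figure:

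- A group main effect averaged over four times includes one time at which the arms have not yet been treated differently, so the effect is diluted.
- If the Bonferroni correction covers the between-arm comparisons at each time, each is tested at less than 0.05.

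What is at stake is the stated 90% for the protocol's own clinically meaningful difference. With no primary contrast fixed, there is also freedom to choose among times and tests after the data are seen.

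**Working it through.** **Method.** Two-sided two-sample t-test power from the noncentral t, with noncentrality d·√(n/2) and 2n − 2 degrees of freedom.

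**1. The plan's own figure.** d = 20/25 = 0.8, level 0.05. Power is 0.902 at 34 and 0.964 at 45, and 34 is the smallest n that reaches 0.90. Appendix 2: 2 × (25/20)² × (1.96 + 1.28)² = 32.8, rounded up to 33. Both figures reproduce.

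**2. Main effect over all four times, baseline included.** Assume a common SD, a common within-patient correlation ρ (not given in the Protocol), an effect of 0.8 SD at each of the three post-intervention times and zero at baseline. The mean effect is 0.8 × 3/4 = 0.6 SD. The SD of a patient's four-time mean is √((1 + 3ρ)/4). The effective d is the ratio.

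| ρ (assumed) | effective d | power at 34 | power at 45 |
|---|---|---|---|
| 0.3 | 0.6/0.689 = 0.871 | 0.94 | 0.98 |
| 0.5 | 0.6/0.791 = 0.759 | 0.87 | 0.95 |
| 0.7 | 0.6/0.880 = 0.682 | 0.79 | 0.89 |
| 0.9 | 0.6/0.962 = 0.624 | 0.72 | 0.83 |

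**3. Main effect over the three post-intervention times only.** The effect is 0.8 and the SD of the mean is √((1 + 2ρ)/3). For ρ = 0.5, 0.7 and 0.9, power at 34 is 0.98, 0.95 and 0.92. Including baseline is what causes the loss in step 2.

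**4. Bonferroni over three time-point t-tests.** Level 0.05/3 = 0.0167, d = 0.8: 0.80 at 34 and 0.91 at 45. The divisor of three is an assumption. At 45, divisors of 2, 4 and 6 give 0.93, 0.89 and 0.86.

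**5. SD equal to 25% of each arm's own mean.** With control at 100 and RM at 120, the SDs are 25 and 30. Then d = 20/√((25² + 30²)/2) = 20/27.61 = 0.724. At 0.05, power is 0.84 at 34 and 0.92 at 45. The support is Table 2, where SD/mean after intervention is:

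- RM: 12.8/51.4 = 0.249, 11.2/49.9 = 0.224, 10.9/49.7 = 0.219
- control: 7.2/29.6 = 0.243, 8.1/30.6 = 0.265, 8.1/30.9 = 0.262

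**6. Steps 4 and 5 together.** d = 0.724 at 0.0167: 0.70 at 34 and 0.84 at 45.

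**7. A baseline-adjusted post-intervention mean.** The residual SD is √((1 + 2ρ)/3 − ρ²). For ρ from 0.3 to 0.8 it falls from 0.666 to 0.476. The effective d is then about 1.20 to 1.68 starting from 0.8, or about 1.09 to 1.52 starting from 0.724. Power at 34 exceeds 0.99 throughout.

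**The case against.** The strongest reply is that nothing stated is miscalculated and that each shortfall is conditional on a reading. Most of this stands.

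- **Bonferroni.** The correction need not touch the primary comparison. The t-tests are supplementary, no divisor is stated, and the correction sentence follows the ANOVA sentence, so it may refer to pairwise comparisons within that model. Table 2 marks time points at P < 0.05 and P < 0.01, not at 0.0167.
- **SD.** The 25% is given once, as a fraction of a single mean. If 20% and 25% both refer to the overall mean (arms at 90 and 110, SDs 22.5 and 27.5), d is 0.796 and power at 34 is still 0.90. The example table is described as resting on 7 patients per group, too few to settle how the SD scales or whether 25% is cautious.
- **Losses.** A reader might infer that about 10 women per arm are expected to be lost, leaving about 35. The text makes this an allowance. The Data Presentation Plan's example has 40 and 41 completers, Appendix 2 allows 10%, and with much missing data all randomised women would be analysed.
- **SAP.** The scope of a multiplicity correction is often left to a SAP, which is not at hand.

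The reply does not remove the mismatch. The Protocol itself states both the sample size and the analysis, and the test behind the first is not identified as primary in the second. Nor does falling back on the single main-effect P-value secure 90%: if baseline is averaged in, step 2 shows less than 0.90 at 34 for correlations of 0.5 and above.

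**Conclusion.** The point holds as a mismatch between the powered test and the stated analysis. It is not an arithmetic error: 34 per group is correct for its inputs.

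Power at 34 per group is 0.87, 0.79 and 0.72 for a main effect including baseline, at assumed correlations of 0.5, 0.7 and 0.9. It is 0.80 for three Bonferroni t-tests, 0.84 for arm-specific SDs alone, and 0.70 for those two together. At the 45 enrolled, the corresponding values are 0.95, 0.89 and 0.83; 0.91; 0.92; and 0.84.

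A reader might infer that the trial is underpowered, with power of 0.80 or less at 34 and 0.84 at 45. The documents do not support that as a property of this plan. It needs both a three-way Bonferroni correction on the primary comparison and an SD proportional to each arm's mean, and neither is fixed in the text. Either feature alone leaves at least 0.91 at 45. That the Table 2 main effect includes baseline is likewise an inference from its layout.

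The practical risk is also limited if the true effect resembles the example table (51.4 against 29.6 at 3 minutes), which is far above 20%. What is lost is a power statement that can be tied to a named primary test.

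**What to change.** In the Statistical analysis section:

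1. Name one primary contrast: the RM minus control difference in mean Com_dyn over 3, 10 and 20 minutes, adjusted for baseline Com_dyn, tested once at two-sided 0.05. A log scale is optional; it would express the result as a percentage, as the 20% target is expressed, and would accommodate an SD that grows with the mean.
2. Confine Bonferroni to the separate time-point comparisons, state how many there are, and label them supportive.
3. Restate the power for the primary contrast, giving the assumed within-patient correlation and saying which mean the 20% and 25% refer to.

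The cost is a few sentences. Enrolment and measurements do not change, since all four Com_dyn readings are already planned. If separate time-point tests are kept as primary instead, their power must be restated at the corrected level, and it will be less favourable than the present figure.

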For each patient we will have four data files:

1. Demographic intra- and post-operative patient data (appendix 3)
2. Mechanical ventilation data (appendix 4)
3. Haemodynamic data (appendix 5)
4. Blood gas data (appendix 6)

Data Presentation Plan

Number of eligible women and number of women excluded before randomization (lets say X):

Possible reasons for exclusion:

[figure not shown]
X1 women could decline participation and choose regional anesthesia, X2 could have emergency surgery, X3 will have active asthma, X4 will have BMI >40, X4 will be < 18 years old, X5 will suffer arterial hypertension etc. If we add: $X1+X2+X3+X4+X5+... Xi=X$

Finally we will include 45 patients in each group.

Number of women that will complete the study = F (For example 40 women in the RM group and 41 women in the Control group)

Give reasons for not complete the study: Heart rate >110bpm, Low arterial blood pressure, hypertension, asthmatic attack during the surgical procedure etc.

Flow chart:

If all, or almost all of the patients will complete the study (we will have the most of the measurements in each time point) we will use a per protocol analysis. If we have many missing data we will use an intention to treat analysis of data (ITT). According to ITT analysis of data I will use all the data of all the randomized patients regardless of whether they completed the trial or not. For the missing values I will use the “last observation carried forward” (LOCF) approach

Patient characteristics should be similar between the two groups (table 1). If not we will have to mention the differences and this would be a serious limitation of our study.

Intraoperative characteristics (time to delivery, anesthesia duration, estimated blood lose, administration of crystalloids and/or colloids, administration of blood products and intraoperative use of ephedrine should be similar between the two groups (table 1).

The length of hospital stay and the possible differences between the two groups should be mentioned (table 1). The number of patients that will suffer postoperative pulmonary complications (mainly pneumonia, diagnosed with chest radiogram and clinical evaluation) and possible differences between the two groups should also be mentioned. Pneumothorax would be a serious adverse event, which could have a strong relationship with the RM manipulation of the patients and should be recorded. See adverse event section below.

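### The protocol chooses between per-protocol and intention-to-treat after the missing data are seen, with no threshold, and fills gaps only by LOCF

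*Protocol*

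**What the plan says.** The rule stands in the Data Presentation Plan, in the paragraph at the flow chart. The condition for per-protocol is "If all, or almost all of the patients will complete the study", which the text glosses as having most of the measurements at each time point. The other branch reads "If we have many missing data we will use an intention to treat analysis of data (ITT". Under that branch all randomised women are analysed, and the missing-data method is "For the missing values I will use the “last observation carried forward” (LOCF) approach". No number defines either condition, and neither analysis is called primary or sensitivity.

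Other sections bear on who would be missing:

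- Statistical analysis justifies 45 per arm by a fear of many protocol violations, described as "removal women from protocol mainly due to hemodynamic instability".
- Removal of Patients from therapy links the RM to falls in blood pressure, but does not expect them to be serious. It also lists causes that can arise in either arm.
- Efficacy and Safety issues names instability during the RM as a safety issue and removes women with serious instability from the study.
- Blinding procedure has two analysts: the primary investigator, who can find each allocation, and a blind statistician. Their results should agree.

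**The concern.** The analysis set for the primary comparison should not depend on something seen only once the data are in. Here it does, and the deciding terms are loose enough for the same data to support either choice. One of the two people analysing the data has access to the allocation.

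The choice matters because the branches can be wrong in different ways. If women leave because they did not tolerate the RM, per-protocol keeps the RM women who did, and the comparison is no longer between randomised groups.

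LOCF has its own problem in this design, because the RM falls between the baseline and the 3-minute readings. A woman removed during the RM has only a reading at zero PEEP before the RM, and that would stand in for all three later readings, pulling the difference toward zero. A woman lost after 3 minutes has her early gain carried to 10 and 20 minutes, which can favour RM. In both cases the mixed ANOVA treats filled values as observed and so misstates precision.

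**Working it through.** **1. The plan's own figure.** Inputs from Statistical analysis: "Two tailed P-values <0.05 will be considered statistically significant"; power 0.90; "Clinically meaningful difference between the two groups is 20% of the mean value"; "SD of the observed lung compliance is 25% of the mean value (rather generous". So d = 20/25 = 0.8.

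- Appendix 2 formula: 2 × (25/20)² × (1.96 + 1.28)² = 32.8, so 33 per group.
- Two-sample t-test (noncentral t): power 89.3% at 33 and 90.2% at 34. This reproduces "we will need minimum 34 patients per group for this study to have adequate power".
- At 45 per arm, power is 96.4%. The room for loss is 45 − 34 = 11 per arm (24%).

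The sample size is sound. The point concerns the analysis rule.

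**2. Which branch applies to the protocol's own example?** The Data Presentation Plan illustrates 40 RM and 41 control completers: 81 of 90, a 10% loss. That can be called nearly all women completing, or a lot of missing data. The Table 3 caption carries the same 40 and 41, which hints at analysing completers, but it is marked as an example.

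**3. LOCF on the example means (Table 2).** Assumption: all removals are in the RM arm, before the 3-minute reading.

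- RM mean after the maneuver: (51.4 + 49.9 + 49.7)/3 = 50.3.
- Control: (29.6 + 30.6 + 30.9)/3 = 30.4. Difference: 20.0 ml/cmH2O, from unrounded means.
- RM baseline: 33.6. Fall in the RM mean with k women filled: (k/45) × (50.3 − 33.6).
- k = 5: 1.9 (about 9% of the difference). k = 10: 3.7 (about 19%), leaving 20.0 − 3.7 = 16.3.

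**4. LOCF at the planned effect.** Same assumption, with arms equal at baseline, a flat control arm and unchanged SD. Expected effect = 20% × (1 − m/45), tested by the t-test of step 1 with 45 per arm.

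| RM women removed (m) | Effect, % of mean | d | Power |
|---|---|---|---|
| 0 | 20.0 | 0.80 | 96.4% |
| 5 | 17.8 | 0.71 | about 92% |
| 11 | 15.1 | 0.60 | about 81% |

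**5. Per-protocol selection.** Simulation of 20,000 trials with no true effect. The m RM women ranked lowest on a tolerance variable are dropped; its correlation with compliance is assumed to be 0.3 to 0.5. No controls are dropped.

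| RM women dropped (m) | Bias, % of mean | Type I error |
|---|---|---|
| 2 | 0.6 to 1.2 | 5.1% to 5.8% |
| 5 | 1.6 to 2.7 | 5.8% to 8.1% |
| 11 | 3.1 to 5.1 | 8.9% to 15.1% |

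The documents give neither removal counts by arm nor any such correlation, so these rows show a range and are not a forecast.

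**6. Who counts as a non-completer?** Removal of Patients from therapy sets a heart-rate limit of above 120 persisting after delivery. The Data Presentation Plan lists above 110 as a reason for not completing. The two give different per-protocol sets.

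**The case against.** - **Per-protocol is conditional.** A reader might infer that it is the unconditional default. It is not: it applies only when nearly all women complete, and then the two sets almost coincide (5.1% to 5.8% with 2 removed). This stands. The weakness is the missing threshold.
- **Arm-related removal is not established.** A reader might infer that women will leave because of the RM. The protocol does not expect the RM's haemodynamic effect to be serious, it names vena cava syndrome, blood loss, tachycardia and asthma as other causes, and its example is nearly balanced. It gives no reasons for the 5 missing RM women. The link is plausible only.
- **The LOCF shift may not be bias for every target.** If a removed woman went back to her earlier settings (the protocol does not say), her true later readings might lie near her baseline. An analysis by allocation with continued readings would then show a similar dilution. This stands for early removals. It does not answer the false precision, or the carrying forward of a 3-minute gain.
- **The conclusion would hold on the example means.** With 10 women filled, 16.3 ml/cmH2O remains, over half the control mean of 30.4 and well above the 20% threshold. This also stands, although the preliminary data are described as 7 women per group and are a weak basis.
- **A blind statistician repeats the analysis.** Agreement checks the calculation. It does not settle which population both analysts use.

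**Conclusion.** The concern holds as a fault in a stated rule. The primary population depends on the observed amount of missing data without a threshold, and LOCF is the only method given for the gaps. It should be fixed because the choice governs the primary comparison, and the protocol's own example of a 10% loss does not settle which branch applies.

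The likely damage is moderate and its direction is open. Early RM removals under LOCF pull toward no difference. A 3-minute gain carried forward, or per-protocol selection by tolerance, can favour RM. At an effect like that in Table 2 the conclusion would probably survive. At the planned 20% effect, 5 early RM removals leave power at about 92%, and 11 take it to about 81%, below the intended 90%. All of this assumes removals in the RM arm only, before 3 minutes.

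A reader might go further and infer that the result would be reversed, or that the investigators mean to pick the favourable set. The documents support neither: they show only that the choice is left open.

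**What to change.** 1. Name all randomised women, analysed as allocated, as the single primary analysis set, whatever the amount of missing data.
2. Replace LOCF with a likelihood-based mixed model on all observed readings (MIXED in the planned SPSS), and state that it assumes data are missing at random. Enter baseline as one of the readings, so that a woman with no later reading still contributes.
3. Keep per-protocol, and LOCF if wanted, only as labelled sensitivity analyses.
4. Where feasible, keep recording the scheduled readings in women who leave the assigned ventilation while still anaesthetised. This matters most if removal follows tolerance, because missing at random is then doubtful.
5. Reconcile the two heart-rate limits (above 120 and above 110), since they decide who is a non-completer.

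The cost is protocol wording, slightly more analysis work and a few extra recordings in removed women. No larger sample is needed: at d = 0.8, power is 96.4% with 45 per arm and 94.5% with outcomes on only 40 and 41.
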